Appendix 2. Columbia-Suicide Severity Rating Scale (C-SSRS): Since Last Visit

# COLUMBIA-SUICIDE SEVERITY RATING SCALE (C-SSRS)

Since Last Visit

Version 1/14/09

### Posner, K.; Brent, D.; Lucas, C.; Gould, M.; Stanley, B.; Brown, G.; Fisher, P.; Zelazny, J.; Burke, A.; Oquendo, M.; Mann, J.

Disclaimer:

This scale is intended to be used by individuals who have received training in its administration. The questions contained in the Columbia-Suicide Severity Rating Scale are suggested probes. Ultimately, the determination of the presence of suicidal ideation or behavior depends on the judgment of the individual administering the scale.

Definitions of behavioral suicidal events in this scale are based on those used in The Columbia Suicide History Form, developed by [name] and [name], Conte Center for the Neuroscience of Mental Disorders (CCNMD), New York State Psychiatric Institute, [name]. (Oquendo M. A., Halberstam B. & Mann J. J., Risk factors for suicidal behavior: utility and limitations of research instruments. In M.B. First [Ed.] Standardized Evaluation in Clinical Practice, pp. 103 -130, 2003.)

For reprints of the C-SSRS contact [name]., New York State Psychiatric Institute, [name]; inquiries and training requirements contact [contact]

 $\textcircled{\mbox{\sc c}}$  2008 The Research Foundation for Mental Hygiene, Inc.  $$\rm UMBIA$$ 

SUICIDAL IDEATION		
Ask questions 1 and 2. If both are negative, proceed to "Suicidal Behavior" section. If the answer to question 2 is "yes", ask questions 3, 4 and 5. If the answer to question 1 and/or 2 is "yes", complete "Intensity of Ideation" section below.		e Last sit
1. Wish to be Dead Subject endorses thoughts about a wish to be dead or not alive anymore, or wish to fall asleep and not wake up. Have you wished you were dead or wished you could go to sleep and not wake up?	Yes	No
If yes, describe:		
2. Non-Specific Active Suicidal Thoughts General, non-specific thoughts of wanting to end one's life/commit suicide (e.g., "I've thought about killing myself" ) without thoughts of ways to kill oneself/associated methods, intent, or plan during the assessment period. Have you actually had any thoughts of killing yourself ?	Yes	No
If yes, describe:		
3. Active Suicidal Ideation with Any Methods (Not Plan) without Intent to Act Subject endorses thoughts of suicide and has thought of at least one method during the assessment period. This is different than a specific plan with time, place or method details worked out (e.g., thought of method to kill self but not a specific plan). Includes person who would say, "I thought about taking an overdose but I never made a specific plan as to when, where or how I would actually do it…and I would never go through with it." Have you been thinking about how you might do this?	Yes	No □
If yes, describe:		
4. Active Suicidal Ideation with Some Intent to Act, without Specific Plan Active suicidal thoughts of killing oneself and subject reports having some intent to act on such thoughts, as opposed to " I have the thoughts but I definitely will not do anything about them." Have you had these thoughts and had some intention of acting on them?	Yes	No □
If yes, describe:		

 
5. Active Suicidal Ideation with Specific Plan and Intent Thoughts of killing oneself with details of plan fully or partially worked out and subject has some intent to carry it out. Have you started to work out or worked out the details of how to kill yourself? Do you intend to carry out this plan? If yes, describe:

	Yes	No
INTENSITY OF IDEATION	 	
The following features should be rated with respect to the most severe type of ideation (i.e., 1-5 from above, with 1 being the least severe and 5 being the most severe).  Most Severe Ideation:	M	ost vere
Type # (1-5) Description of Ideation		
Frequency How many times have you had these thoughts? (1) Less than once a week (2) Once a week (3) 2-5 times in week (4) Daily or almost daily (5) Many times each day		
Duration		
When you have the thoughts, how long do they last?(1) Fleeting - few seconds or minutes(4) 4-8 hours/most of day(2) Less than 1 hour/some of the time(5) More than 8 hours/persistent or continuous(3) 1-4 hours/a lot of time(5) More than 8 hours/persistent or continuous	_	
Controllability	1	
Could/can you stop thinking about killing yourself or wanting to die if you want to?(1) Easily able to control thoughts(4) Can control thoughts with a lot of difficulty(2) Can control thoughts with little difficulty(5) Unable to control thoughts(3) Can control thoughts with some difficulty(0) Does not attempt to control thoughts		

Deterrents		
Are there things - anyone or anything (e.g., family, religion,	, pain of death) - that stopped you from	
wanting to die or acting on thoughts of committing suicide?		
(1) Deterrents definitely stopped you from attempting suicide	(4) Deterrents most likely did not stop you	
(2) Deterrents probably stopped you	(5) Deterrents definitely did not stop you	
(3) Uncertain that deterrents stopped you	(0) Does not apply	
Reasons for Ideation		
What sort of reasons did you have for thinking about wanting		
the pain or stop the way you were feeling (in other words yo		
how you were feeling) or was it to get attention, revenge or a (1) Completely to get attention, revenge or a reaction from others	(4) Mostly to end or stop the pain (you couldn't go	
on		
(2) Mostly to get attention, revenge or a reaction from others	living with the pain or how you were feeling)	
(3) Equally to get attention, revenge or a reaction from others couldn't go on	(5) Completely to end or stop the pain (you	
and to end/stop the pain	living with the pain or how you were feeling)	
	(0) Does not apply	
SUICIDAL BEHAVIOR		
(Check all that apply, so long as these are separate events; must	ask about all types)	
Actual Attempt:		
A potentially self-injurious act committed with at least some wish to die,		
oneself. Intent does not have to be 100%. If there is any intent/desire to		
suicide attempt. There does not have to be any injury or harm,		er while gun
is in mouth but gun is broken so no injury results, this is considered an at		E.
Inferring Intent: Even if an individual denies intent/wish to die, it may be example, a highly lethal act that is clearly not an accident so no other inte		
window of a high floor/story). Also, if someone denies intent to die, but t		
inferred.	,	
Have you made a suicide attempt?		
Have you done anything to harm yourself?		
Have you done anything dangerous where you could have d	lied?	
What did you do?		
Did you as a way to end your life?		
Did you want to die (even a little) when you?		
Were you trying to end your life when you?		
Or did you think it was possible you could have died fi		
Or did you do it purely for other reasons / without ANY inte		feel better,
get sympathy, or get something else to happen)? (Self-Injuriou	us Behavior without suicidal intent)	
If yes, describe:		
Has subject engaged in Non-Suicidal Self-Injurious Behav	/ior?	
Interrupted Attempt:		
When the person is interrupted (by an outside circumstance) from starting	g the potentially self-injurious act (if not for that, actual	attempt
would have occurred).		
Overdose: Person has pills in hand but is stopped from ingesting. Once t interrupted attempt. Shooting: Person has gun pointed toward self, gun is		
trigger. Once they pull the trigger, even if the gun fails to fire, it is an atte		
from ledge. Hanging: Person has noose around neck but has not yet starte		
Has there been a time when you started to do something to a	end your life but someone or something stoppe	d you
before you actually did anything?		
If yes, describe:		
Aborted Attempt:		
When person begins to take steps toward making a suicide attempt, but s	tops themselves before they actually have engaged in an	y self-
destructive behavior. Examples are similar to interrupted attempts, excep		
something else.		
Has there been a time when you started to do something	to try to end your life but you stopped yours	elf before
you actually did anything?		

If yes, describe:

### **Preparatory Acts or Behavior:**

Acts or preparation towards imminently making a suicide attempt. This can include anything beyond a verbalization or thought, such as assembling a specific method (e.g., buying pills, purchasing a gun) or preparing for one's death by suicide (e.g., giving things away, writing a suicide note).

Have you taken any steps towards making a suicide attempt or preparing to kill yourself (such as collecting pills, getting a gun, giving valuables away or writing a suicide note)? If yes, describe:

### **Suicidal Behavior:**

Suicidal behavior was present during the assessment period?

Suicide:

### Answer for Actual Attempts Only

Actual Lethality/Medical Damage:

- 0. No physical damage or very minor physical damage (e.g., surface scratches).
- 1. Minor physical damage (e.g., lethargic speech; first-degree burns; mild bleeding; sprains).
- 2. Moderate physical damage; medical attention needed (e.g., conscious but sleepy, somewhat responsive; second-degree burns; bleeding of major vessel).
- 3. Moderately severe physical damage; *medical* hospitalization and likely intensive care required (e.g., comatose with reflexes intact; thirddegree burns less than 20% of body; extensive blood loss but can recover; major fractures).
- 4. Severe physical damage; *medical* hospitalization with intensive care required (e.g., comatose without reflexes; third-degree burns over 20% of body; extensive blood loss with unstable vital signs; major damage to a vital area).

#### 5. Death

### Potential Lethality: Only Answer if Actual Lethality=0

Likely lethality of actual attempt if no medical damage (the following examples, while having no actual medical damage, had potential for very serious lethality: put gun in mouth and pulled the trigger but gun fails to fire so no medical damage; laying on train tracks with oncoming train but pulled away before run over).

0 = Behavior not likely to result in injury

1 = Behavior likely to result in injury but not likely to cause death

2 = Behavior likely to result in death despite available medical care

© 2008 Research Foundation for Mental Hygiene, Inc.

C-SSRS—Since Last Visit (Version 1/14/09)

Appendix 3. InQoL

# HOW YOUR MUSCLE CONDITION AFFECTS YOU

This questionnaire is designed to see how your muscle condition affects you.

The first section will ask about your symptoms and how much they affect your life. NOT all the symptoms mentioned may apply to you in which case please indicate this where asked and move on to the next question.

The second section will be questions asking how you feel about your physical ability, independence, relationships, how you feel emotionally and the way you look.

The third and last section will ask about any treatment you might receive. You will be asked about the effects this treatment has had and the effects you expect it to have.

The information you provide will help doctors to understand your problems. This will mean they can work towards better care and treatment for you.

Please read the questions carefully and answer all the questions that apply to you.

[figure not shown]
Thank you.

### SECTION 1

### QUESTION 1:- YOUR MUSCLE WEAKNESS

1 Do you have any muscle weakness due to your muscle condition? By weakness we mean any weakness in your face, arms, hands, legs and feet.

PLEASE CHECKONE BOX

### a) How much weakness would you say you have in the muscles affected by your condition?

PLEASE CIRCLE ONE NUMBER

Very little	Some	A fair	A	A	A lot	An
		amount	moderate	considerable		extreme
			amount	amount		amount
1	2	3	4	5	6	7

### b) Does your muscle weakness cause difficulties in your life at the moment?

PLEASE CIRCLE ONE NUMBER

None at	Some	A fair	A	A	Very	An
all		amount	moderate	considerable	many	extreme
			amount	amount		amount
0	1	2	3	4	5	6

[figure not shown]
### c) How important to you are any difficulties caused by your muscle, weakness?

Not at all	Slightly	Reason-	Moderate-	Consider-	Very	Extremely
important	important		ly	ably	important	important
		important	important	important		
0	1	2	3	4	5	6

### QUESTION 2:- YOUR PAIN

### 2 Do you have any pain as a result of your muscle condition?

PLEASE CHECKONE BOX

### a) How much pain would you say you have at the moment?

PLEASE CIRCLE ONE NUMBER

V	ery little	Some	A fair	A	A	A lot	An
			amount	moderate	considerable		extreme
				amount	amount		amount
	1	2	3	4	5	6	7

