## 6. STUDY PROCEDURES

Every attempt should be made to schedule the visits on the day specified in the Schedule of Activities. In order to provide optimal testing conditions and consistency in endpoint measurements, at visits when the functional assessments, imaging and clinical laboratory assessments are scheduled to be completed at the same visit, the visit should be completed on two days within the visit window and at approximately the same time of day in the order described below.

There is no window for Day 1(first dosing day). The visit window for the additional treatment visits is  $\pm 3$  Day. For the final follow up visit, the window is  $\pm 3$  days. The window for the PK assessments post dosing at 2 hours is  $\pm 30$  minutes. If the infusion rate is decreased (following an infusion site reaction) the PK/PD assessment should be collected at the time of infusion completion and flush (within a  $\pm 30$  minute window). Subjects are required to be observed for 1 hour after administration of PF-06252616.

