#### On Day 2 of Visit 3 (Day 1)- prior to dosing,

- **Functional assessments:** Must be conducted in the following order: 4SC, 2MWT, 10-meter walk/run, TUG, and PUL.
- **Needle muscle biopsy:** Following the Functional assessments, a needle muscle biopsy of the tibialis muscle will be performed.

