# 6.8. Follow up: For Cohort 1, Visit 19 (Day 449±3) and for Cohort 2 and 3, Visit 11 (Day 225±3)

This visit will occur over 2 days.

- Physical Examination, including Nose and Throat Mucosal Exam.
- **Pregnancy Test**: A highly sensitive urine pregnancy test will be performed on all female subjects
- **Diary Cards:** For collection of first day of each menstrual cycle for WOCBP.
- Contraception Review: Confirmation of use of acceptable forms of contraception
- Weight
- Vital Signs: Supine blood pressure, pulse rate, respiratory rate, and oral temperature.
- 12-lead ECG: ECGs will be performed in triplicate
- Echocardiogram
- Clinical laboratory testing:

- Hematology with complete blood count and differential, comprehensive metabolic panel (sodium, potassium, chloride, carbon dioxide, blood urea nitrogen, creatinine, calcium, glucose, total protein, albumin, total bilirubin, AST, ALT, alkaline phosphatase) gamma-glutamyl transferase (GGT), prothrombin time (PT), activated partial thromboplastin time (aPTT), creatine kinase, amylase, cardiac troponin I. Urinalysis.
- Serum ferritin, serum iron, % transferrin saturation, TIBC: fasting blood collection
- Horomone Testing: LH, FSH, estrogen in WOCBP
- GLDH
- Fecal Occult Blood: Fecal sample is to be collected at home within 1 week prior to scheduled visit.
- C-SSRS
- **MRI-liver**: Liver MRI will be obtained for iron accumulation
- **MRI-muscle:** WB-MRI and dedicated thigh MRI will be performed for muscle quantity and quality
- **DXA Whole Body:** Whole body DXA will be performed for lean body mass assessment.
- **DXA Spine and Hip:** Spine and hip DXA will be performed for BMD.
- **Functional assessments:** Must be conducted in the following order: Respiratory function (FVC, FEV1, MIP, MEP), 4SC, 2MWT, 10-meter walk/run, TUG, strength assessment (MMT, hand-held dynamometry) and PUL.
- **Needle muscle biopsy:** Following WB-MRI and functional assessments, a needle muscle biopsy of the tibialis muscle will be performed.
- Quality of Life assessments
  - InQol
  - SF-36
- Immunogenicity sample collection.
- PD sample collection
- PK sample collection

- Adverse Event monitoring
- Infusion site reaction monitoring
- Concomitant medication

6.9. Follow-up: For Cohort 1, Visit 20 (Day 561±3) and for Cohort 2 and 3 Visit 12 (Day 337±3)

- Physical Examination, including Nose and Throat Mucosal Exam.
- **Pregnancy Test**: A highly sensitive urine pregnancy test will be performed on all female subjects

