### QUESTION 3:- HOW TIRED YOU FEEL

### 3 Do you feel tired/ fatigued as a result of your muscle condition?

PLEASE CHECKONE BOX

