### a) How much tiredness/ fatigue would you say you have at the moment?

PLEASE CIRCLE ONE NUMBER

Very little	Some	A fair	A	Α	A lot	An
		amount	moderate	considerable		extreme
			amount	amount		amount
1	2	3	4	5	6	7

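### The section 6 visit lists put InQoL before the muscle biopsy at Visit 3 but after it at later visits, so biopsy soreness can enter the change in its current-pain item

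*Protocol*

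**What the plan says.** Protocol 2.2.2.3 and SAP 4.2.2.4 make mean change from baseline in InQoL and SF-36 a secondary endpoint. SAP 8.2.2 models patient-reported outcomes as change from Visit 3, and SAP Appendix 1 plans a separate InQoL pain table (Table 14.1.1.110). InQoL is not scheduled at Visit 2, so Visit 3 is its only pre-dose value.

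InQoL Question 2 (Protocol Appendix 3) opens with a gate, "Do you have any pain as a result of your muscle condition". Item 2a then asks "How much pain would you say you have at the moment", rated 1 to 7.

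Protocol Section 6 says that visits combining functional, imaging and laboratory assessments should be spread over two days, "at approximately the same time of day in the order described below". In 6.3 the quality-of-life forms close the main pre-dose list. The biopsy comes in the separate block for Day 2 of Visit 3: "Following the Functional assessments, a needle muscle biopsy of the tibialis muscle will be performed". In 6.8 the biopsy entry reads "Following WB-MRI and functional assessments, a needle muscle biopsy of the tibialis muscle will be performed", and the quality-of-life entry comes directly after it. The lists in 6.9 and 6.15 have the same sequence.

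The Schedule of Activities for all three cohorts puts InQoL and SF-36 in the functional assessments block. Footnote a of the Schedule and Protocol 7.7 ask for functional testing before the biopsy whenever possible.

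**The concern.** A change score assumes that both forms were completed under the same conditions. A site that works down the lists collects the reference InQoL before the biopsy and the later forms shortly after a needle has been passed into the leg muscle. Item 2a asks about pain now and, unlike the gate, does not repeat the link to the muscle condition. A subject with some disease pain passes the gate and may then count soreness from the procedure. On this item a higher score means more pain, so any such effect would look like worsening.

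The effect could not be removed in analysis. There is no concurrent control, and without a Visit 2 form there is no lead-in InQoL change to compare with. The listed order also differs between cohorts at Visit 11, so any effect there would be mixed with dose.

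**Working it through.** The plan states no figure on this point, so the check sets the passages side by side.

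**Step 1: listed order by visit**

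| Visit | Protocol section | InQoL relative to biopsy, by the list |
|---|---|---|
| Visit 3, all cohorts | 6.3 | Before (biopsy in the Day 2 block) |
| Visit 11, Cohort 1 | 6.3 | Biopsy scheduled, timing not stated; the Day 2 block is headed for Visit 3 only |
| Visit 11, Cohorts 2 and 3; Visit 19, Cohort 1 | 6.8 | After |
| Visit 12, Cohorts 2 and 3; Visit 20, Cohort 1 | 6.9 | After |
| Early Withdrawal | 6.15 | After, if performed |
| Final extension visit (27, 22 or 18) | 6.12 | No biopsy |

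**Step 2: which SAP contrasts are reached**

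SAP 8.2.2 defines four intervals, all measured from Visit 3. InQoL is not collected at Visits 7 or 15, so only two intervals have InQoL data.

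- Visit 11 minus Visit 3: the listed order reverses for Cohorts 2 and 3, which is 8 + 8 = 16 of the 20 planned subjects (20 and 40 mg/kg). For the 4 subjects in Cohort 1 (5 mg/kg) the text does not put InQoL after the biopsy.
- Visit 19 minus Visit 3: the listed order reverses for the 4 Cohort 1 subjects.

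Visits 12 and 20 are not among the modelled intervals.

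**Step 3: size, by assumption only**

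Let q be the share of subjects whose item 2a rating is raised by the biopsy, and s the rise in categories. The shift in mean change is q × s. The documents give neither value. With s = 1:

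- q = 1%: 0.01 × 1 = 0.01
- q = 10%: 0.10 × 1 = 0.10
- q = 50%: 0.50 × 1 = 0.50

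In a cohort of 8, one subject moved by one category shifts the cohort mean by 1/8 = 0.125. Subjects who answer no at the gate contribute nothing, so q cannot exceed the share who report pain from their condition. These figures apply to item 2a alone; the documents do not say how the items combine into a pain score. They give no standard deviation for InQoL either, so the shift cannot be put in standard-error units without a further assumption.

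**The case against.** The strongest reply is that the lists are not a clock order. Section 6.12 lists dosing before PK and PD sampling, while the extension schedule's footnote makes those samples predose. Section 6.2 lists biomarker blood after the afternoon biopsy, while 7.2.1 wants it in the morning after a fast. Where sequence matters the protocol says so directly, as it does for the functional battery and the biopsy, and no such sentence governs the questionnaires. Section 6 says should, and footnote a calls its order preferred. The Schedule's grouping would place InQoL before the biopsy at every visit. This stands in part: the actual order may vary, and a reversal at the site is not established. It also shows that the protocol can be read two ways. Section 7.8 describes quality of life separately from the functional assessments, so the Schedule's grouping does not settle the matter.

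The second reply is the gate. Biopsy soreness is not pain from the muscle condition, and items 2b and 2c ask about difficulties in life and their importance, which brief soreness is less likely to move. Protocol 7.9 describes local anaesthetic, a skin incision under 0.5 cm and no recovery time. This limits the effect but does not exclude it, because item 2a does not repeat the attribution. The figure of less than 1% in 1.12.7 covers the complications listed there, not ordinary soreness.

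A reader might also extend the point to fatigue, weakness or SF-36. The documents do not support that:

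- Fatigue has its own gate, "Do you feel tired/ fatigued as a result of your muscle condition", and the functional tests precede InQoL in the Visit 3 list as well as the later ones, so tiredness from testing is largely common to both forms.
- No mechanism is apparent for the weakness item.
- The SF-36 pain, energy and tiredness items refer to the past four weeks.

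**Conclusion.** The listed order of InQoL and biopsy reverses between the reference visit and the later biopsy visits, and the Schedule's grouping points the other way. The passages need to be reconciled. Biopsy soreness can enter the change in current pain among subjects with disease pain. In the Visit 11 minus Visit 3 contrast, any effect would be mixed with dose, because the lists put InQoL after the biopsy for 20 and 40 mg/kg but do not do so for 5 mg/kg.

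Three stronger conclusions might be inferred and are not supported. First, the documents do not show that procedure pain does bias the endpoint: that needs sites to follow the lists and subjects to misattribute soreness, and neither is known. Second, not every post-treatment form is affected, since the final extension visits have no biopsy. Third, the Cohort 1 Visit 11 form cannot be called pre-biopsy, because the timing of that biopsy is not stated.

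The size is unknown. The range of 0.01 to 0.50 category rests wholly on the assumed 1% to 50% of subjects and a one-category rise. This is a possible inconsistency in one secondary endpoint, worth correcting because the correction costs so little.

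**What to change.** In Protocol 6.3, 6.8, 6.9, 6.12 and 6.15, give InQoL one stated position before functional testing and biopsy at every visit, with SF-36 alongside for convenience. Bring the Schedule of Activities into line with that position.

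For visits already completed, establish from source, where available, whether the form preceded the biopsy, and flag post-biopsy forms in the patient-reported outcome listing.

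No new assessment is needed. The cost is an edit to the lists and a small source check. Forms already completed in the old order cannot be repaired and remain flagged. For subjects whose Visit 3 form followed the functional tests, later forms will also have moved relative to those tests, which the listing should note.
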